9.3.2 Regulatory Reporting for Studies Not Conducted Under DMID-Sponsored IND

As this study will not be conducted under an IND, MEDWATCH will be used to report related AEs. DMID should be copied simultaneously when an alternate method of reporting is utilized.

9.3.3 Reporting of Pregnancy

Participants of child-bearing potential will be counseled to continue using acceptable forms of birth control as well as condoms during the study period. If a participant becomes pregnant during the study, dosing will be discontinued immediately. A pregnancy reporting form will be completed for any study participant who becomes pregnant during the study period. The site will maintain contact with pregnant study participants to obtain pregnancy outcome information. The pregnant participant will be followed until delivery or until the end of pregnancy (in the case of miscarriage or pregnancy termination). Infants born to these study participants will also be monitored for SAEs (congenital anomalies or other birth defects) and other complications for up to two months after birth. Pregnancy reporting forms will be limited to collecting data on the following information:

- prior maternal history including congenital abnormalities or pregnancy complications;
- estimated date of conception;
- estimated and actual date of delivery or end of pregnancy;
- pregnancy outcome (live birth, stillbirth, miscarriage or elective termination);
- mode of delivery;
- maternal complications; and
- neonatal complications (i.e., lethal or nonlethal congenital abnormality).

Pregnancies occurring in study participants will be reported via AdvantageEDCSM on the Pregnancy Report form.

9.4 Type and Duration of Follow-up of Participants after Adverse Events

AEs and SAEs will be followed from the time of study treatment through resolution even if this extends beyond the study reporting period, Visit 2. Resolution of an AE/SAE is defined as the return to pretreatment status or stabilization of the condition with the expectation that it will remain chronic.

Follow-up procedures, evaluations, and outcomes will be recorded on the appropriate data collection form.

•

9.5 **Halting Rules**

Further enrollment will be halted for DSMB review/recommendation if any two participants experience an adverse event that is judged to be Severe (Grade 3) and related to study product.

DMID retains the authority to suspend additional enrollment and administration of study product during the entire study, as applicable.

9.6 Safety Oversight (ISM plus DSMB)

An Independent Safety Monitor (ISM) at each clinical research site will oversee the safety of research participants at that site and will provide independent written evaluation of SAEs and related Grade 3 AEs to the DMID Clinical Project Manager and DMID Medical Monitor. The ISM will serve as an independent consultant for the site PI on participant-related issues. The ISM will communicate with the site PI and study PIs to resolve any issues.

Safety oversight will be conducted by a DSMB that is an independent group of experts that monitors participant safety and advises DMID. The DSMB members will be separate and independent of study personnel participating in this trial and should not have scientific, financial or other conflict of interest related to the study. The DSMB will consist of members with appropriate expertise to contribute to the interpretation of the data from this trial.

The DSMB will review study progress and participant, clinical, and safety data at the following time points:

- At specified times during the course of study as defined in the DSMB Charter,
- Ad hoc when a halting rule is met, for immediate concerns regarding observations during the study, or as needed.
- A final closeout meeting will be held at the end of the study after the database is locked and when the final study report is available.

The DSMB will operate under the rules of a DMID-approved charter that will be written at the organizational meeting of the DSMB. As an outcome of each review/meeting, the DSMB will make a recommendation as to the advisability of proceeding with study administrations (as applicable), and to continue, modify, or terminate the study. The DSMB members will meet at specified times during the course of the study as defined in the DSMB Charter.

DMID or the DSMB chair may convene the DSMB on an ad hoc basis according to protocol criteria or if there are immediate concerns regarding observations during the course of the study. The DMID Medical Monitor is empowered to stop enrollment and study treatment if adverse events that meet the halting criteria are reported. The DMID Medical Monitor will be

responsible for reviewing SAEs in real time. The DSMB will review SAEs on a regular basis and ad hoc during the study.

10 CLINICAL MONITORING

10.1 Site Monitoring Plan

DMID, the sponsoring agency, or its designee will conduct site-monitoring visits as detailed in the clinical monitoring plan and in accordance with DMID policies. Site monitoring is conducted to ensure that the human subject protections, study and laboratory procedures, study intervention administration, and data collection processes are of high quality and meet sponsor, ICH/GCP guidelines and applicable regulations; and that the study is conducted in accordance with the protocol, protocol-specific manual of procedures and applicable sponsor standard operating procedures. Monitoring visits will include, but are not limited to, inspection of study facilities, review of regulatory files, accountability records, CRFs, IC forms, printouts of medical and laboratory reports from the electronic medical records (EMR) system, and protocol and GCP compliance. Site monitors will have access to the study site, study personnel, and all study documentation according to the DMID-approved site monitoring plan. Study monitors will meet with Pls to discuss any problems and actions to be taken and document visit findings and discussions.

Site visits will be made at standard intervals as defined by DMID and may be made more frequently as directed by DMID.

11

STATISTICAL CONSIDERATIONS

11.1 Study Hypotheses

There is one planned formal test of hypothesis which compares amoxicillin to placebo with respect to the primary efficacy outcome measure. The hypothesis test compares the proportion of participants with eradication of GV in each study arm through Visit 2 (Day 15-21) as assessed by NAAT.

The null hypothesis for the comparison is that there is no difference in proportions between study arms, with a two-sided alternative. The test will be conducted using a Pearson Chi-Square test with Yates continuity correction at the 5% two-sided significance level. The hypothesis will be tested in the Intent-to-Treat (ITT) efficacy analysis population for the primary analysis and repeated as a secondary analysis in the Per-Protocol (PP) analysis population.

11.2 Sample Size Considerations

Sample size calculations are based on detecting a decrease in GV colonization rate from 80% among participants receiving placebo to as large as 44% among participants receiving amoxicillin. Using the two-sided Pearson Chi-Square test with Yates continuity correction, significance level of 0.05, and assuming an amoxicillin to placebo allocation ratio of 1:1, 82 women (41 in each arm) would provide 90% power to detect a difference in colonization rates of 36% (i.e. 44% colonization rate in the amoxicillin arm).

Assuming a 15% drop-out rate between enrollment and the ToC visit approximately 98 women will need to be randomized to obtain 82 women evaluable for the primary analysis. Assuming 40% of women without BV will have a positive NAAT test for GV at screening, approximately 245 women without BV will need to be screened to randomize 98 women in the study.

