PI Principal Investigator
PK Pharmacokinetics
PP Per-Protocol
QA Quality Assurance
QC Quality Control

SAE Serious Adverse Event/Serious Adverse Experience

SDCC Statistical and Data Coordinating Center

SI Site Investigator

SIC Screening Informed Consent
SOP Standard Operating Procedure
STD Sexually Transmitted Disease
STI Sexually Transmitted Infection

T. vaginalis Trichomonas vaginalis

ToC Test of Cure US United States

PROTOCOL SUMMARY

Title: A Randomized, Double-Blind, Placebo Controlled, Phase 2

Study to Assess Treatment of Gardnerella vaginalis Vaginal

Colonization with Amoxicillin

Phase:

Population: Approximately 245 healthy women will be screened to enroll

98 participants (to achieve 82 evaluable participants) ages 18-45 with no evidence of vaginitis (yeast, trichomonas, bacterial vaginosis (BV)); presence of Gardnerella vaginalis (GV) detected by NAAT; willing to use condoms during the study;

not currently menstruating.

Number of Sites: Two US clinics: University of Alabama at Birmingham and

Wake Forest University Health Sciences

Study Duration: Approximately 24 months is anticipated for enrollment and

completion of participation.

Participation Duration: It is anticipated that each participant will be part of the protocol

for approximately 22 days (screening visit, enrollment visit,

and 1 follow-up visit).

Description of Agent or

Intervention:

Amoxicillin 2 x 250 mg capsules PO bid 7 days or placebo

Objectives: Primary: To determine if treatment with amoxicillin eradicates

GV in women who are colonized/infected with GV but have no

clinical evidence of BV.

Secondary:

To evaluate the safety and tolerability of amoxicillin

compared to placebo.

Exploratory:

To determine the demographic and behavioral factors

associated with vaginal colonization of GV;

Description of Study Design:

This is a randomized, double-blind, placebo-controlled Phase 2 study. It is anticipated that 245 women will be screened in order to enroll 98 participants to achieve 82 evaluable participants. Participants will be randomized to amoxicillin 2 x 250 mg PO bid or placebo, for 7 days. Participation will include three visits in total – a Screening Visit, an Enrollment Visit, and 1 Follow- up visit. Total participation for each woman will be approximately 22 days.

Estimated Time to Complete Enrollment:

Approximately 24 months

Schematic of Study Design:

Total N: ~245 screened to enroll 98 (to achieve 82 evaluable)

Study Visit 0: Screening

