11.4.1 Analysis Populations

Intent-to-Treat (ITT) Population: This analysis population includes all randomized participants.

The ITT population will be used as the primary efficacy analysis population.

Safety Population: This analysis population includes all randomized participants who received at least one dose of study treatment.

Per-Protocol (PP) Population: This analysis population includes all randomized participants who met all inclusion/exclusion criteria, are evaluable, adhered to the assigned study treatment regimen (as defined below), and returned to the study site for the ToC visit within the specified window (Visit 2 [Window: Day 15 -21]) and did not experience any of the following after enrollment:

- Unprotected vaginal sexual intercourse between Visit 1 and Visit 2
- New pregnancy reported by the subject
- Receipt of any antibiotic or intravaginal microbicide other than study drug

Participants are deemed evaluable if their BV and GV status can be determined at screening and their GV status can be determined at Visit 2. Participants who are missing Gram stain, GV NAAT, or Amsel results at screening are not evaluable. Participants who are missing GV NAAT results at the Visit 2 are not evaluable.

A Participant is considered adherent to the study treatment regimen if she uses at least 80% of the scheduled doses (i.e. at least 12 of the 14 doses) of study treatment, as assessed by the number of pills returned. If pill count cannot be assessed, participant report will be used to assess adherence.

In the unlikely event of an error in randomization or study product administration, participants will be grouped by the formulation they actually received in the PP and Safety analyses but will be grouped by their intended randomized assignment in the ITT analysis.

NAAT Screening Population: This analysis population includes all screened women who are evaluated for GV by NAAT.

The NAAT screening population will be used as the exploratory efficacy analysis population.

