11.4.4 Efficacy Analysis Plan

11.4.4.1 Primary Efficacy Analysis

For the primary analysis of the efficacy of amoxicillin in women who are infected with GV but have no clinical evidence of BV, the number and proportion of women with eradication of GV at Visit 2 (Day 15-21) will be summarized overall and by treatment group. The point estimates for the arm-specific proportions and difference in proportions as well as corresponding 95% confidence intervals will be reported. A test of hypothesis will be conducted using Pearson Chi-Square test with Yates continuity correction at the 5% two-sided level of significance level to

formally compare the treatment groups. The primary analysis will be performed in the ITT analysis population and repeated as a secondary analysis in the PP analysis population.

Eradication of GV is defined by a negative NAAT result for GV at Visit 2 (Day 15-21). Participants who have a missing GV NAAT result at the ToC visit are excluded from the PP analyses, and will be classified as treatment failures in the ITT analyses.

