6.5. Missing Data

Subjects who are not evaluable will be excluded from the PP population.

Participants who have a missing GV NAAT result at the TOC visit are excluded from the PP analyses. For the ITT population, participants who have a missing GV NAAT result at the TOC visit will be classified as treatment failures.

For ITT population, the Worst-Case imputation will also be explored. In this analysis, participants who have a missing GV NAAT result at the TOC visit in Amoxicillin arm will be classified as treatment failures while those who in placebo arm will be classified as cures.

Only GV eradication status will be imputed.

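### The stated 90% power belongs to 82 women with a Visit 2 result, not to the primary ITT analysis of 98 (about 87–88% at 15% missing); and 245 is derived as women without BV but used as the total screened

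*Protocol*

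**What the plan says.** **Power.** Protocol 11.2, repeated in SAP 5, assumes GV colonisation of 80% on placebo and 44% on amoxicillin, 1:1 allocation, and a two-sided Yates-corrected chi-square test at 0.05. It states that "82 women (41 in each arm) would provide 90% power to detect a difference in colonization rates of 36" percentage points. After a 15% drop-out allowance, it says "approximately 98 women will need to be randomized to obtain 82 women evaluable for the primary analysis".

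**Primary analysis.** Protocol 11.4.1 defines ITT as all randomised participants and says "The ITT population will be used as the primary efficacy analysis population". The same section makes evaluability a condition of the per-protocol set and says "Participants who are missing GV NAAT results at the Visit 2 are not evaluable". Under Protocol 11.4.4.1, women without that result "will be classified as treatment failures in the ITT analyses". SAP 6.5 agrees: "For the ITT population, participants who have a missing GV NAAT result at the TOC visit will be classified as treatment failures".

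**Screening.** Protocol 11.2 assumes that 40% of women without BV are GV-positive and concludes that "approximately 245 women without BV will need to be screened to randomize 98 women in the study". The Protocol Summary says "It is anticipated that 245 women will be screened in order to enroll 98 participants to achieve 82 evaluable participants", without that restriction. The study schematic, Protocol 4, Protocol 5 and SAP 4.1 use 245 in the same unrestricted way.

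**The concern.** The sample-size paragraph describes a complete-case comparison: 82 women with a result, and drop-outs simply lost. In the planned primary analysis nobody is lost. The women without a Visit 2 result stay in the denominator as failures in both arms, so the number analysed rises from 82 to 98 while the difference between arms shrinks. These effects pull power in opposite directions and need not cancel. A reader who takes 90% as the power of the primary test has the wrong number, and is not shown that the true one depends on how many results are missing and in which arm.

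The two uses of 245 agree only if no screened woman is excluded before the 40% is applied. Protocol 4 makes women with vaginitis at screening screen failures, and Protocol 7.1 has the remaining specimens discarded when on-site microscopy shows an infection. A total of 245 screened would therefore be expected to yield fewer than 98 randomised.

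**Working it through.** **Inputs (Protocol 11.2).** Eradication is 1 − colonisation: 0.56 on amoxicillin and 0.20 on placebo. The test is Yates-corrected chi-square, two-sided, α = 0.05. Drop-out is 15%. Stated sizes are 82 (41 per arm) and 98 (49 per arm).

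**Methods.** Exact power is the sum of the binomial probabilities of all pairs of arm counts for which the Yates-corrected p-value is below 0.05. The formula value is the usual two-proportion power at the continuity-corrected size n′ = (n − 1/d)²/n, where d is the difference in proportions.

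**1. The plan's own figures reproduce.**
- 41 per arm, 0.56 v 0.20: 90.3% exact. By formula, n′ = (41 − 1/0.36)²/41 = 35.6, giving 89.6%.
- Drop-out: 41/0.85 = 48.2, rounded up to 49 per arm, so 98.
- Screening: 98/0.40 = 245.

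**2. Power of the primary ITT analysis.** If a share m is missing equally in both arms and non-informatively, eradication is 0.56(1 − m) v 0.20(1 − m), with 49 per arm:

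| Missing | Amoxicillin | Placebo | Difference | Exact | Formula |
|---|---|---|---|---|---|
| 10% | 0.504 | 0.180 | 0.324 | 90.3% | 90.1% |
| 15% | 0.476 | 0.170 | 0.306 | 87.6% | 87.0% |
| 16.3% (16 of 98) | 0.469 | 0.167 | 0.301 | 86.8% | 86.1% |
| 20% | 0.448 | 0.160 | 0.288 | 84.4% | 83.4% |

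The 16.3% row is the plan's own 82 with a result out of 98.

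**3. Sensitivity (exact, 49 per arm).** The unequal splits are illustrations and are not in the documents.
- 17% missing on amoxicillin, 13% on placebo: 0.83 × 0.56 = 0.465 v 0.87 × 0.20 = 0.174, power 83.9%.
- 13% on amoxicillin, 17% on placebo: 0.87 × 0.56 = 0.487 v 0.83 × 0.20 = 0.166, power 90.7%.
- If 80%/44% already counted missing as failure: 0.56 v 0.20, power 94.7%.

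**4. Screening.** If a share v of screened women is excluded before the 40% applies, the total needed is 245/(1 − v), and 245 screened yields 245 × (1 − v) × 0.40. The documents give no v, so these values are assumptions:

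| v | Total to screen | Randomised from 245 |
|---|---|---|
| 10% | 273 | 88 |
| 20% | 307 | 78 |
| 30% | 350 | 69 |

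**The case against.** The plan contains no arithmetic slip: 90%, 98 and 245 each reproduce on their own terms. The power loss is under three points (90.3% to 87.6%), which lies within the uncertainty of inputs for which the plan gives no source. If amoxicillin colonisation were 42.5% instead of 44%, ITT eradication at 15% missing would be 0.85 × 0.575 = 0.489 v 0.170, and exact power is back at 90.0%. The plan does not say whether 80% and 44% are rates among women with a result; on the other reading power is 94.7%. The ITT rule is stated openly, and Protocol 4 already ties the 82 to the test-of-cure visit. Women who withdraw consent before receiving product may be replaced (Protocol 5.3.4), so the ITT count could slightly exceed 98. On screening, every count is approximate, nothing caps screening at 245, and the size of any shortfall rests on an assumed share.

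Much of this stands. The loss is modest and conditional, and the screening point concerns consistency and feasibility, not inference. It does not remove the mismatch. If 80%/44% already counted missing as failure, inflating 82 to 98 would have been unnecessary, so on either reading the sample-size paragraph does not describe the primary test. Evaluable is also a defined term, and by that definition it excludes women whom the primary analysis includes.

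**Conclusion.** Both parts hold. The 90% is right for 82 women with a Visit 2 result and wrong as a description of the primary analysis. That analysis has about 87–88% power at 15% missing, and 86.8% (exact) if only 82 of 98 have a result. These figures assume equal, non-informative drop-out, 49 per arm, and 80%/44% as rates among women with a result, which is how the drop-out inflation reads. The shortfall is modest but sensitive to which arm loses more women.

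The figure of 245 is correct only as a count of women without BV. Its use as the total screened is inconsistent with its derivation. How far 245 would fall short cannot be determined from the documents, and the practical consequence is workload and timeline.

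**What to change.** - **Protocol 11.2 and SAP 5:** state that 90% power applies to the 82 women with a Visit 2 GV result, and remove the description of them as evaluable for the primary analysis.
- **Same places:** add the power of the primary ITT analysis with missing counted as failure: about 87–88% with 49 per arm and 15% missing, assuming equal, non-informative drop-out. Say that 80%/44% are rates among women with a result, and preferably show the 10% and 20% missing values beside it.
- **Wherever 245 appears** (protocol summary and schematic, Protocol 4, 5 and 11.2, SAP 4.1 and 5): label it as women without BV, and give a separate total-screened figure with its assumed exclusion rate. That rate should also cover yeast and trichomonas, which are exclusions too, and say whether eligible women who decline (a category in SAP Table 7) are allowed for.

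The cost is wording only. It needs no added randomised patients and no change to the test, the populations or the missing-data rule.

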11.3 Planned Interim Analyses

11.3.1 Safety Review

The DSMB may review study progress and participant safety data at specified times during the course of study, as defined in the DSMB Charter. The study will be monitored to determine if any of the safety halting rules described above in Section 9.5 are met. The halting rules do not utilize any statistical criteria and no formal hypothesis testing is planned to occur for the safety and enrollment data reviews

11.3.2 Efficacy Review

There are no planned interim efficacy analyses for this study.

11.4 Final Analysis Plan

A separate statistical analysis plan document will be generated that will contain the details of the analyses. This section outlines the major components of the analyses.

11.4.1 Analysis Populations

Intent-to-Treat (ITT) Population: This analysis population includes all randomized participants.

The ITT population will be used as the primary efficacy analysis population.

Safety Population: This analysis population includes all randomized participants who received at least one dose of study treatment.

Per-Protocol (PP) Population: This analysis population includes all randomized participants who met all inclusion/exclusion criteria, are evaluable, adhered to the assigned study treatment regimen (as defined below), and returned to the study site for the ToC visit within the specified window (Visit 2 [Window: Day 15 -21]) and did not experience any of the following after enrollment:

- Unprotected vaginal sexual intercourse between Visit 1 and Visit 2
- New pregnancy reported by the subject
- Receipt of any antibiotic or intravaginal microbicide other than study drug

Participants are deemed evaluable if their BV and GV status can be determined at screening and their GV status can be determined at Visit 2. Participants who are missing Gram stain, GV NAAT, or Amsel results at screening are not evaluable. Participants who are missing GV NAAT results at the Visit 2 are not evaluable.

A Participant is considered adherent to the study treatment regimen if she uses at least 80% of the scheduled doses (i.e. at least 12 of the 14 doses) of study treatment, as assessed by the number of pills returned. If pill count cannot be assessed, participant report will be used to assess adherence.

In the unlikely event of an error in randomization or study product administration, participants will be grouped by the formulation they actually received in the PP and Safety analyses but will be grouped by their intended randomized assignment in the ITT analysis.

NAAT Screening Population: This analysis population includes all screened women who are evaluated for GV by NAAT.

The NAAT screening population will be used as the exploratory efficacy analysis population.

